Male and female veterans of all ethnicities will be sought to participate. All participants must meet the following criteria during intake or analysis: 1) be between 18 and 64 years of age; 2) meet DSM-5 criteria for current Post Traumatic Stress Disorder, as assessed by study staff using the Clinician Administered PTSD Scale-5 (CAPS-5); 3) be fluent in English; 4) have vision corrected to be able to see a computer display clearly; 5) be able to provide informed consent and be able to follow verbal or written instructions; 6) assessed as not a significant harm to self or others.

SUBJECT EXCLUSION CRITERIA

All participants admitted to the unit will be allowed to partake in the study. Those with contraindications to the fMRI will complete behavioral only tasks. The following exclusion criteria will be applied to all participants during analysis: younger than 18 or older than 65; self-reported PTSD symptoms for less than six months; diagnosed seizure disorder; history of stroke; Cushing's syndrome; history of moderate to severe traumatic brain injury (TBI); electroconvulsive therapy within 5 years; history of chemotherapy for cancer; contraindications to fMRI; current pregnancy; diagnoses of schizophrenia, schizoaffective disorder, delusional disorder, organic psychosis, bipolar disorder, or depressive disorder with psychosis as assessed with SCID-5-RV (and not stabilized or in remission); symptoms meeting criteria for a substance use disorder within the previous 30 days (assessed through SCID-5, Alcohol Use Disorders Identification Test score > 8); meets criteria for acute psychiatric or medical admission; assessed as significant risk of harm to self or others; use of non-prescribed narcotics; acute cardiac difficulties (unless cleared by a cardiologist); psychotic disorders not otherwise specified assessed with SCID-5-RV; subjects using benzodiazepines (they will be given the opportunity to discontinue and must be off for at least two weeks prior to the beginning of the study); psychotropic medications must be stabilized for at least two weeks prior to the beginning of the study and remain stabilized throughout the entire duration of the study; if changed, the subject may be dropped from the study at the discretion of the research staff; positive drug tests during the course of the study will be grounds for disenrollment from the study. Given the high prevalence of psychotropic medication usage in

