PTSD, use of antidepressants or anxiolytics will not be an exclusion criterion. The subject may be dropped from the study at the discretion of the research staff.

USE OF SPECIAL/VULNERABLE POPULATION:

For this study, we will be recruiting individuals with PTSD. As individuals with mental illness can be a vulnerable population, we will take particular care to prevent undue coercion, protect the subjects' confidentiality, and obtain informed consent. All subjects will be informed of the purpose of the study, the potential value of the study to society, the lack of value to the subject personally, and potential risks to the subject. It will be explained to the subject that he or she is under no obligation whatsoever to participate, and that if he or she wishes to discontinue involvement at any time during the study he or she is free to do so without penalty. Individuals receiving treatment for PTSD or any medical treatment from the VA will be assured that their treatment will in no way be affected by their choice to participate or not participate, or their choice to withdraw at any time.

STUDY DESIGN:

This study consists of two primary treatment groups: 1) Trauma Management Therapy, comprised of exposure therapy (EXP) and social and emotional rehabilitation (SER) (N = 44), and 2) veterans receiving Prolonged Exposure Therapy (PE), comprised of exposure therapy plus skills-focues group therapy based in Acceptance and Commitment Therapy and informed by Dialectical Behavioral Therapy (EXP + ACT/DBT) (N = 44). All participants will be recruited within the Salem VAMC residential PTSD unit, a 13-bed facility offering residential care for veterans with PTSD. The unit will exclusively offer one of the two arms of treatment (EXP+SER or EXP+ACT/DBT) at any particular time, and the order of offering will be randomized across the year. Thus, assignment to treatment arm will be depend upon the treatment arm being currently offered.

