Individuals meeting inclusion and exclusion criteria will be invited to participate in the study protocol, consisting of a battery of neuroimaging tasks completed prior to and following completion of treatment. Individuals choosing to participate in the study will be asked to lie in an MRI scanner, located at the Fralin Biomedical Research Institute at Virginia Tech Carilion in Roanoke, VA, and play simple games consisting of viewing objects on a digital screen and making choices by pressing handheld buttons. The scanner detects regional cerebral blood flow accompanying changes in brain activation when subjects are perceiving emotional or reward-related stimuli. Subjects will be asked to participate in three tasks of this nature during the scanning session, depending on their comfort level and time available. Following the initial fMRI scanning session, participants will begin treatment (TMT or PE). Following completion of treatment, participants will undergo the above-described fMRI scanning procedures a second time.

PROCEDURES:

All research activities will be conducted by Salem VAMC research staff members at Fralin Biomedical Research Institute at Virginia Tech Carilion (FBRI) and/or Salem VAMC. The PI or

a clinically experienced senior staff member will accompany all subjects with PTSD throughout their participation in the study.

I. Recruitment

Veterans may learn of this study by being informed by residential clinical staff, receiving a letter from research staff at the Salem VA Medical Center (attached), word of mouth, or when inquiring about residential treatment at the Salem VA Medical Center. During the initial patient screening phone call for the PTSD residential unit, the VA staff member will also inform the patient of the study. If a veteran is interested in participating in research, study staff will contact him/her by phone to provide information about the study and conduct initial eligibility screening. In addition, letters will be mailed to Veterans who have expressed interest in the study. This letter (attached) will provide the Veteran with the contact information for study staff. At the request of clinical PTSD RRTP staff, a letter (see attached) including a description of the study and contact information for study staff will be provided to the PTSD RRTP clinical coordinator for the purpose of including it in each Veterans' clinical welcome packet.

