Individuals who remain eligible for the study following clinical intake assessments, research intake assessments, review of medical record and assessment for contraindications to MRI will be invited to participate. Once the participants complete all pre-treatment study procedures, all participant data will fall under intention-to-treat analysis, where dropouts and non-compliant participants may be followed up on with post-treatment assessments and follow-up assessments as with all other

participants. Veterans who are found to not meet inclusion criteria following pre-treatment assessment may be unenrolled from the study at the discretion of study staff. All Veterans who are removed from the study will be paid for all study procedures completed to that point.

Veterans who may be eligible for Neuroscience of Social Behavior (PC-0002) study will be asked to complete a Release of Information form to share their contact information with PC-0002 study staff. A copy of relevant de-identified assessment data (see attached list) may also be released to the PC-0002 staff once written informed consent has been obtained by them from the Veteran.

The research staff will explain the study to the veteran and will answer any questions he/she may have prior to obtaining written informed consent.

Veterans will be assured that their choice to participate, or not, will have no effect on their treatment, clinical care or relationship with their clinician.

II. Assessment and Intervention

Initial Visit: Consent and Pretreatment Procedures

After written informed consent has been obtained, participants will begin study procedures.

Participants will complete pretreatment interviews, including the CAPS-5, SCID-5-RV with a trained clinical interviewer prior to beginning treatment.

Participants will complete the study questionnaires on paper during the first week at FBRI and/or at the Salem VA Medical Center (questionnaire battery including, for example, PCL, SAS-SR, AQ, ITS, etc.). Additionally, acceptability of treatment will be assessed through measures of treatment credibility and satisfaction after three weeks of treatment and the end of treatment, respectively.

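### The protocol applies its exclusion list at analysis, and that list includes two events that can follow assignment; read literally this contradicts its intention-to-treat sentence, and the SAP names no analysis set

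*Protocol*

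**What the plan says.** Protocol, Subject Exclusion Criteria, lets everyone admitted to the unit take part and then says: "The following exclusion criteria will be applied to all participants during analysis". Most of the list is history or baseline status. Two items are tied to the study period. Psychotropic medication must stay stable for the whole study, and "if changed, the subject may be dropped from the study at the discretion of the research staff". Also, "positive drug tests during the course of the study will be grounds for disenrollment from the study". The section closes with an unqualified line: "The subject may be dropped from the study at the discretion of the research staff".

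Contraindication to fMRI is on the same list, although the start of that paragraph says: "Those with contraindications to the fMRI will complete behavioral only tasks".

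Protocol, Procedures, I. Recruitment, says that after pre-treatment procedures "all participant data will fall under intention-to-treat analysis", and mentions dropouts and non-compliant participants in that context.

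Protocol, Study Design, sets the arm by calendar period: "The unit will exclusively offer one of the two arms of treatment (EXP+SER or EXP+ACT/DBT) at any particular time".

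The SAP is one paragraph: a regression of CAPS-5 and SAS-SR (primary) on treatment and time (pre, post), with the Time x Treatment interaction as the test and age as covariate. It gives no analysis set, no exclusion rule and no handling of disenrolled veterans.

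**The concern.** The exclusion section states a rule about analysis, and so does the intention-to-treat sentence. For a veteran who completes pre-treatment procedures and later changes medication or has a positive drug test, the literal wording of the two gives opposite answers. Two analysts could build different primary datasets from the same documents.

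This matters because both events come after assignment and could be affected by the assigned treatment. Dropping after a medication change is discretionary, and because the unit runs one arm at a time, staff can know the arm when they decide. If such veterans left the analysis, the comparison of TMT with the control arm would no longer be between the groups as assigned, and the bias could go either way.

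**Working it through.** **1. Sections side by side**

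| Place in the protocol | Subject of the sentence | Does it settle who is analysed? |
|---|---|---|
| Subject Exclusion Criteria | Exclusions, applied at analysis | Yes, literally: listed veterans are out |
| Same section, the two in-study items | Dropping, disenrolment | Enrolment consequence; silent on data |
| Study Design ("Individuals meeting inclusion and exclusion criteria will be invited to participate in the study protocol") and Consent Procedures | Screening before treatment | No; cannot cover later events |
| Recruitment | Intention-to-treat after pre-treatment procedures | Yes: everyone is in |
| Follow-up | Terminated or dropped patients assessed at 1 week, 3 and 6 months | No; data collection, and the SAP contrast is pre to post |
| Sample Size | Subjects who meet criteria and finish | No; does not say whether the rest are analysed |

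The SAP adds nothing on this point. Two in-study items is a minimum: undated items such as acute admission, risk of harm, pregnancy or non-prescribed narcotics could also arise after assignment if judged at analysis.

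**2. The plan's own figure**

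2 x 44 = 88, and 88 x 1.5 = 132, as stated. So 132 - 88 = 44 enrolled veterans, 44/132 = 33%, are expected not to meet criteria or not to finish. The protocol does not split these by reason or arm.

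**3. Illustration of size (removal shares and gaps are assumed)**

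- Let p be the share removed in an arm and g the mean change of those kept minus that of those removed, in SD of change. The mean of those kept differs from the mean of the whole arm by p x g.
- Bias in the treatment contrast = pT x gT - pC x gC. With the same g in both arms this is (pT - pC) x g.
- Assume a 5 to 15 point difference in removal and g of 0.5 to 1.0. Low end: 0.05 x 0.5 = 0.025. High end: 0.15 x 1.0 = 0.15.
- With two time points the Time x Treatment contrast is a difference in mean change. With 44 per arm left after removals, SE = sqrt(2/44) = 0.213 SD of change.
- Bias/SE: 0.025/0.213 = 0.117 and 0.15/0.213 = 0.704.
- Two-sided 5% test, no true effect, noncentral t with 86 df: rejection rates of 5.15% and 10.7%. The midpoint (0.10 x 0.75 = 0.075; 0.075/0.213 = 0.352) gives 6.4%. Using 85 df for the age covariate changes none of these at the precision shown.

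Veterans are treated as independent, and assignment by unit period is ignored.

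**The case against.** The two in-study clauses speak of dropping and disenrolment, not of deleting data. Elsewhere the protocol uses similar language for participation: the Data and Safety Monitoring Plan for withdrawal, and Risks & Benefits for removal from the protocol with referral to care. The intention-to-treat sentence addresses analysis directly and could reasonably govern a loosely drafted list. The Follow-up section requires terminated patients to be assessed, which makes little sense if their data were to be discarded. All of this stands, and it makes the benign reading the more likely intention. It does not remove the explicit statement that the list is applied at analysis, and no sentence says which governs.

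On fMRI, the Exclusion, Recruitment and Procedures sections all keep ineligible veterans in the study with tasks outside the scanner. An imaging-only limit is the natural reading, so this item is secondary.

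On size, nothing in the documents supports a 5 to 15 point difference in removal over six weeks of residential treatment. That is correct; the figures show scale and do not estimate an effect.

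A reader might go further in three ways that the documents do not support.

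- **That veterans were in fact removed and the primary result is biased.** No document reports any removal for these reasons.
- **That the 33% measures these exclusions.** It pools ineligibility with non-completion.
- **That the error rate could reach 14.6%.** This needs three assumed extremes together: a 15-point difference, a gap of 1.0 SD of a single score, and a pre-post correlation of 0.7. At that correlation the SD of change is sqrt(2 x 0.3) = 0.775, so the gap is really 1/0.775 = 1.29 SD of change. With the gap in SD of change, the range is 5.2% to 10.7% at any correlation.

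**Conclusion.** The ambiguity is real and affects who enters the primary CAPS-5 and SAS-SR comparison. The exclusion section as worded and the intention-to-treat sentence cannot both be followed for a veteran with a listed in-study event, and the SAP does not choose between them. The wording favours the benign reading without establishing it.

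The actual effect is unknown and may be nil. Under the stated assumptions the inflation runs from negligible (5.2%) to about double the nominal rate (10.7%), and the upper end needs both the largest removal difference and the largest gap. The point should be fixed; confidence is medium, because the conflict rests on a literal reading and no removal is shown.

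**What to change.** Reconcile the exclusion section with the intention-to-treat sentence, and state one clinical analysis set in both protocol and SAP:

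1. Only criteria fixed from data recorded before treatment starts may remove a veteran from the clinical analysis. Apply them from the baseline record with arm label, admission date and outcomes withheld where feasible; the date matters because it reveals the arm.
2. All others who completed pre-treatment procedures are analysed in their assigned arm, whatever their later medication change, drug test or disenrolment. Fit the Time x Treatment model, with age, in a likelihood-based repeated-measures form, so that veterans without post-treatment scores still contribute baseline data.
3. Any per-protocol set is a sensitivity analysis only.
4. Contraindication to fMRI limits the imaging analyses only.
5. Report exclusions and missing outcomes by arm and reason.

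The SAP is written largely in the past tense, so the primary regression should be re-run if anyone was removed for a post-assignment event or for fMRI contraindication.

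The cost is a few sentences, one table and possibly one re-run. The downsides are some dilution of the estimate from non-adherence and some missing post-treatment data, since the protocol says only that dropouts may be followed up with post-treatment assessments. Rules for withdrawing veterans from treatment are unchanged.

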JULY 11, 2022

EFFICACY AND NEURAL MEDIATORS OF RESPONSE TO TRAUMA MANAGEMENT THERAPY FOR PTSD

NCT03449576

EFFICACY AND NEURAL MEDIATORS OF RESPONSE TO TRAUMA MANAGEMENT THERAPY FOR PTSD

Principal Investigator: [name]

Co-Investigators:

[name]
[name]
[name]
[name]
[name]
[name]
[name]
[name]
[name], MSW
[name]

SPONSOR: VA Merit Grant and NIH Award Number UL1TR003015

PURPOSE/OBJECTIVES:

This research is intended to provide data from humans to test the efficacy and examine the neural mediators of response to Trauma Management Therapy (TMT) among veterans with post-traumatic stress disorder (PTSD).

In this study, our specific aims are to 1) test the efficacy of TMT for the treatment of fear and anxiety symptoms of PTSD as well as the interpersonal dysfunction associated with PTSD, and 2) identify neural mediators of TMT-related reductions in fear and anxiety as well as interpersonal dysfunction in veterans.

Treatment-seeking veterans with PTSD will be randomized into one of two treatments: (i) Trauma Management Therapy, consisting of 12 individual sessions of exposure therapy and 24 group sessions of social and emotional rehabilitation, or (ii) Prolonged Exposure Therapy (PE), consisting of standard 12 sessions of exposure therapy and 24 group sessions of skills-focused group therapy based in acceptance and commitment therapy (ACT) and dialectical behavioral therapy (DBT). Clinician-administered and self-report measures of (i) fear and anxiety symptoms of PTSD, and (ii) interpersonal dysfunction associated with PTSD will be assessed across the course of treatment. We will test the primary hypothesis that the addition of social and emotional rehabilitation to the standard course of exposure therapy leads to greater reduction in interpersonal dysfunction, and evaluate potential neural mediators of efficacy.

Veterans enrolled in the study will undergo functional neuroimaging as they engage in an emotional image viewing task, as well as two social interaction tasks sensitive to aggression and cooperation. The neurobehavioral assessments will be made prior to and following completion of treatment. We will test the hypotheses that pre/post-treatment changes in the response of specific brain regions (detailed below) will mediate the relationship between TMT treatment and

reductions in 1) fear and anxiety during the emotional image task and 2) interpersonal dysfunction during the aggression and cooperation tasks.

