preprogrammed to play the game. While playing the game, subjects will view stimuli representing their options and choices (e.g., slider bar indicating a choice of \$10). Conditions of certain game variants may include one subject challenging his/her partner at a monetary cost to him/herself. Subjects will be compensated, in part, based on their earnings in the exchange games in order to incentivize performance. The scanner will detect changes in regional cerebral blood flow that accompany neural activity during these tasks. The duration of this task is approximately 30 minutes.

Following completion of the imaging/task session, each participant will be transported via VA vehicle or by their own transportation arrangement from the Human Neuroimaging Laboratory at the Fralin Biomedical Research Institute at Virginia Tech Carilion back to the PTSD residential unit at the Salem VAMC.

Psychotherapy Interventions

Treatment will be conducted by Master's or doctoral-level clinicians at the Salem VAMC. All therapists will be trained and experienced with behavioral treatments for psychological disorders, including PTSD. In addition, therapists will undergo 20 hours of clinical training: 10 hours of didactics and discussion, and 10 hours that will consist of running one mock group through each TMT phase and component, and one individual session where an imaginal scene is constructed and administered to a mock patient. Training will be conducted by TMT experts/creators ([name] & [name]), who will be involved in ongoing supervision and consultation throughout the project. Treatment sessions will follow the manual constructed for TMT and therapists will be supervised in weekly sessions (including the use of recordings of sessions). When problems of adherence or quality are detected, reeducation will occur. We will have adherence data at the end of treatment such that determination of overall adherence can be made.

This study includes two treatment arms, described below. Both treatment arms will be administered across 6 weeks, and the TMT group will include 12 sessions of individualized exposure therapy (EXP); while the PE group will have 12 sessions of individualized exposure therapy. The treatments will also differ, in that Trauma Management Therapy will include 24 sessions of group-based sessions targeting social and emotional rehabilitation (SER), while the control condition will include 24 sessions of skills-focused group therapy (ACT/DBT).

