(3) Programmed Practice. The programmed practice component of TMT is implemented as part of the final 7 individual exposure sessions, and is a form of exposure that does not necessitate therapist-accompaniment (i.e., it is "homework"). Homework assignments, like exposure sessions, are geared specifically toward the participant's individual fear pattern. Examples of suitable assignments include watching movies (e.g., *Platoon* or *Hamburger Hill*), visiting war memorials or museums, speaking with other participants or loved ones about war experiences, and visiting airfields or helicopter pads. Experiences should also be devised which require the participant to engage in other feared activities, the avoidance of which may interfere with his or her quality of life. Examples of suitable activities include social events (e.g., parties, having dinner with friends), shopping, attending movies, eating in a restaurant, etc.

(4) Social and Emotional Rehabilitation (SER). This component is conducted in a group modality and will consist of up to 13 participants and one to two clinicians. A highly structured group administered SER component was developed to target the interpersonal difficulties that are often part of PTSD but are not improved by exposure only. These difficulties include social anxiety, social alienation and withdrawal, excessive anger and hostility, explosive episodes, marital and family conflict. SER is implemented in small group sessions and includes basic social skills training, anger management and behavior activation therapy. Components of SER are as follows:

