Our goal is to have 44 subjects in each of the two treatment groups complete this study over the course of four years. From our past experience conducting studies of this complexity with specific inclusion/exclusion criteria, we anticipate needing to enroll 1.5 subjects to achieve 1 subject who meets criteria and finishes the study. Thus, we multiplied our target of 88 subjects by 1.5 to reach our total sample size of **132**.

PROVISIONS FOR MANAGING & REPORTING ADVERSE EVENTS:

During all phases of the study, a doctorate-level clinician will be available for consultation and to help manage any negative reactions that occur in response to the neuroimaging sessions. All study staff working with the patients will be trained in suicide risk assessment, basic suicidal crisis intervention skills, and the study's safety protocol.

If patients exhibit symptoms of significant distress or anxiety at any time during their participation in study procedures at FBRI, they will be guided through clinical techniques to help them regulate their distress. Their session may be terminated if deemed appropriate. If it is determined that they are expressing suicidal/homicidal ideation or thoughts of self-harm or harm to others, clinically

trained staff will work with the veteran to reduce distress and/or acute suicide or homicide risk. When the veteran feels calm and is determined by staff to not be an imminent risk to self or others, they will be escorted back to the residential unit by a trained research staff member via the VA vehicle. If a veteran has driven or ridden in a private vehicle to the appointment and the veteran is deemed stable and safe by staff, they may be allowed to drive their vehicle back to the Salem VA and check in to the residential unit. If at any time clinical staff determine that the Veteran is an imminent risk to self or others and/or not safe to independently drive or ride in a private vehicle, the Veteran will be transported via the VA vehicle or ambulance, whichever is clinically indicated. Study personnel will remain with patients determined to be an imminent risk to self or others until direct hand off to a VA clinician or EMS response is possible.

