JUNE 1, 2023

EFFICACY AND NEURAL MEDIATORS OF
RESPONSE TO TRAUMA MANAGEMENT
THERAPY FOR PTSD
NCT03449576

Analysis of primary clinical outcome hypothesis for D2354-R “Efficacy and Neural Mediators of Response to Trauma Management Therapy for PTSD”

A regression approach was used to test the effect of treatment type (TMT, EXP+EDU) on both primary (CAPS-5 and SAS-SR) and secondary (PCL-5, AQ, ITS) outcome measures across Time (pre-treatment, post-treatment). The Time x Treatment interaction was be used to test whether TMT improves outcomes relative to EXP+EDU, and age was entered as a co-variate as the two treatment arms differed in age at baseline.

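### Treatment is assigned by unit-wide offering period, but the SAP names neither a period nor a participant term; a paired Time x Treatment test is too liberal if change is correlated within period

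*Protocol*

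**What the plan says.** The protocol's Study Design section describes one 13-bed residential unit and states: "The unit will exclusively offer one of the two arms of treatment (EXP+SER or EXP+ACT/DBT) at any particular time". It adds that "the order of offering will be randomized across the year", and concludes: "Thus, assignment to treatment arm will be depend upon the treatment arm being currently offered". The Purpose/Objectives section words this differently: "Treatment-seeking veterans with PTSD will be randomized into one of two treatments". Neither document gives the number or length of the periods.

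On delivery, the Psychotherapy Interventions section says "Both treatment arms will be administered across 6 weeks". For the social and emotional rehabilitation (SER) groups of the TMT arm, the protocol says: "This component is conducted in a group modality and will consist of up to 13 participants and one to two clinicians". The comparator arm also attends group therapy. The Sample Size section says: "Our goal is to have 44 subjects in each of the two treatment groups complete this study over the course of four years".

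The SAP is one short paragraph. It says "A regression approach was used to test the effect of treatment type (TMT, EXP+EDU" and goes on to list the outcomes, two time points (pre and post), the Time x Treatment interaction as the test, and age as covariate. It names no period, cohort or calendar term, no participant term, no clustered variance and no ICC.

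**The concern.** When whole periods are randomised, the chance variation between arms includes variation between periods. A model that treats each veteran as independently assigned leaves that part out.

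For this test, only variation in change matters. A period that is simply more severe at both time points drops out of a paired pre/post contrast. A period in which everyone improves more, or less, does not. The protocol offers plausible routes to such an effect:

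- SER groups can hold as many people as the unit has beds, led by one or two clinicians.
- The integration and relapse-prevention sessions may be adapted to the needs of a particular group.
- Under COVID-19 procedures, pretreatment interviews could move to telephone or video before admission, which could shift baseline for whole stretches of admissions.

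None of these shows that the correlation exists; they show why independence should not be assumed without comment. At stake is the meaning of the p-values and confidence intervals for the primary outcomes, CAPS-5 and SAS-SR.

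**Working it through.** **The plan's own figure.** 2 x 44 = 88 completers, and 88 x 1.5 = 132 enrolled. This reproduces. It is a completer target with an allowance for ineligibility and dropout. It contains no power calculation and no design effect.

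**Inputs from the protocol.** 44 completers per arm, four years (208 weeks), 6-week treatment, one arm on offer at a time.

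**Assumptions, not in the documents.** Two-sided 5% test; 34, 16 or 8 periods (208/6 = 34.7 is the most that 6-week blocks allow; 16 is quarterly, 8 half-yearly); ICC of change 0, 0.05 or 0.10; pre-post correlation 0.5 where pairing is ignored.

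**Paired test, effect shared by the whole period.** Design effect DE = 1 + (m - 1) x ICC, with m = 88/periods. Actual error = 2 x P(Z > 1.96/√DE).

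| Periods | m | DE at ICC 0.05 / 0.10 | Actual error |
|---|---|---|---|
| 34 | 2.59 | 1.079 / 1.159 | 5.9% / 6.9% |
| 16 | 5.5 | 1.225 / 1.450 | 7.7% / 10.4% |
| 8 | 11 | 1.500 / 2.000 | 11.0% / 16.6% |

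At ICC 0, DE = 1 and the error is 5.0%. Simulation (40,000 trials per setting, t-test on change) agrees: 11.1% / 16.7% with 8 periods and 7.4% / 10.3% with 16.

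**Paired test, effect shared only while stays overlap.** Here two veterans' correlation is the ICC times the share of a 6-week stay that they spend together. Admissions must be confined so that each stay fits inside one period. Spacing 88 admissions evenly over 208 weeks would not do: at 34 periods of 6.1 weeks, 98% of stays would run across an arm switch, which the exclusive offering does not allow. With stays confined, DE = 1 + S x ICC, where S is the average summed overlap with others in the same period.

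| Periods | S | DE at ICC 0.05 / 0.10 | Actual error |
|---|---|---|---|
| 34 | 1.67 | 1.083 / 1.167 | 6.0% / 7.0% |
| 16 | 2.44 | 1.122 / 1.244 | 6.4% / 7.9% |
| 8 | 2.04 | 1.102 / 1.204 | 6.2% / 7.4% |

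At 34 periods everyone in a period overlaps almost fully, so this matches the first table apart from whole-number period sizes.

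**Pairing ignored.** The ratio of true to assumed variance becomes (1 - 0.5) x DE. At ICC 0 the error is 2 x P(Z > 1.96/√0.5) = 0.6%. At ICC 0.05 / 0.10, with the effect shared by the whole period, it is 0.8 / 1.0% (34 periods), 1.2 / 2.1% (16) and 2.4 / 5.0% (8). The unpaired test becomes liberal only when DE exceeds 1/(1 - 0.5) = 2.

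**Does a period-level analysis work?** In simulation, a t-test on period-mean change with (periods - 2) df held 4.7 to 5.2%. With age adjustment it gave 5.0 to 6.2%. A random period effect on change with age and Satterthwaite df gave 1.0 to 5.1%, and was conservative with 8 periods (1.0 to 4.5%).

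**The case against.** The strongest reply is that the size is unknown and the large figures rest on a mechanism that the documents do not describe. Errors above 10% need an effect shared by everyone in a period for its whole length, and few periods. The protocol also has features that would limit such effects: 12 individual exposure sessions in each arm, manual-based TMT, weekly supervision and re-education when adherence slips. This stands, and the first table should be read as illustration only.

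Second, a two-sentence SAP that reports a pre/post Time x Treatment test may well be shorthand for a repeated-measures model. Nothing in it excludes a participant effect or clustered errors. This also stands: the text shows an incompletely stated model, not a demonstrably wrong one.

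Third, the SAP reports a baseline age difference between arms, so it was written with data in hand. Replacing the primary model now would itself be a post hoc choice. This stands and shapes the fix.

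What survives is that the randomised unit is documented, the stated model takes no account of it, and analysis by that unit needs only admission and arm-switch dates.

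A reader might go further and infer that the primary p-values are inflated, that the comparison was not randomised, or that period assignment caused the age imbalance. The documents support none of these. The ICC could be zero, the order of offering was to be randomised, and nothing ties the age difference to periods.

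**Conclusion.** The point holds in conditional form and should be fixed. It is certain from the text that assignment is by unit-wide period and that the SAP names neither a period nor a participant term. It follows that a paired Time x Treatment test is too liberal if change is correlated within period. It does not follow that the reported test was too liberal: with zero ICC of change there is no inflation, and without pairing the error is usually conservative.

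Under the assumptions above, the nominal 5% becomes about 6.0 to 7.9% if only overlapping stays share an effect, and 5.9 to 16.6% if whole periods do. Confidence in the gap is high; confidence in its size is low, because the number of periods, the ICC and the pairing are all unstated. The wording in Purpose/Objectives is a minor inconsistency with Study Design.

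**What to change.** 1. State in the SAP that assignment was by offering period, and align Purpose/Objectives with Study Design.
2. State that the analysis is paired, using change scores.
3. Add an analysis that respects the randomised period: either age-adjusted period-mean change compared by arm with about (periods - 2) df, or a random period effect on change with small-sample df. Do not use fixed period effects, since each period has only one arm. Do not rely on a period random intercept alone in the pre/post model, since it cancels from Time x Treatment. If ANCOVA is preferred, put the random period effect on the post-treatment score: stable period differences do not cancel there. In simulation with 8 periods, pre-post correlation 0.5 and no correlation of change, unclustered ANCOVA rejected in roughly 7% / 9% of trials when period explained 5% / 10% of score variance, while the change-score test stayed near 5%.
4. State that with a change-score outcome age adjusts the change (age x Time). An age main effect in complete paired data leaves the interaction estimate as it was, so this is a different adjustment.
5. Report the number and dates of periods per arm and the ICC of change, and say that the conclusion is limited if periods are few.
6. Label the period-level analysis as post hoc or a sensitivity analysis, beside the stated model.

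The work is SAP wording and one further fit, using each veteran's admission date and the arm-switch dates. The statistical cost is precision. With 34 / 16 / 8 periods the critical t is 2.04 / 2.14 / 2.45 against 1.99, so intervals widen by about 2% / 8% / 23% even at zero ICC. The difference detectable with 80% power rises from 0.60 SD of change to 0.62 / 0.64 / 0.72 at zero ICC, and to 0.64 / 0.71 / 0.88 at ICC 0.05 with the effect shared by the whole period. The random-effect model is conservative with 8 periods.
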